9.2.4. Clinically Notable Adverse Events Based on Customized MedDRA Queries

There are 9 categories of clinically notable TEAEs (ie, categories of erythropenia [anemia], neutropenia, thrombocytopenia, CMV infections, EBV infections, hyperlipidemia, QT prolongation, thromboembolic events, fungal infections) that, in particular, are of scientific and medical interest specific to itacitinib and the GVHD population. The lists of MQs are in [Appendix B](#) through [Appendix F](#).

Within each category, the number and percentage of participants with at least 1 event occurring during treatment tabulated by MedDRA PT will be summarized. Summaries of clinically notable AEs based on customized MQs will be provided by category, PT, and the maximum severity.

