8.3. Safety Assessments

8.3.1. Adverse Events

Adverse events will be monitored from the time the participant signs the ICF until at least 30 days after the last dose of study treatment. Adverse events that begin or worsen after informed consent should be recorded on the Adverse Events Form in the eCRF regardless of the assumption of a causal relationship with study treatment(s). Conditions that were already present at the time of informed consent should be recorded on the Medical History Form in the eCRF.

Adverse events (including laboratory abnormalities that constitute AEs) should be described using a diagnosis whenever possible rather than by individual underlying signs and symptoms.

Adverse events will be reported by the participant (or, when appropriate, by a caregiver, surrogate, or the participant's legally authorized representative). The investigator and any qualified designees are responsible for detecting, documenting, and recording events that meet the definition of an AE or SAE and remain responsible for following-up on AEs that are serious, considered related to the study treatment/procedures, or that caused the participant to discontinue study treatment. Care will be taken not to introduce bias when detecting AEs and/or SAEs. Open-ended and nonleading verbal questioning of the participant, such as "How are you feeling?" is the preferred method to inquire about AE occurrences. Adverse events may also be detected when they are volunteered by the participant during the screening process or between visits, or through physical examinations, laboratory tests, or other assessments. The definition, reporting, and recording requirements for AEs are described in Section 9.

All SAEs will be recorded and reported to the sponsor or designee within 24 hours. The investigator will submit any updated SAE data to the sponsor within 24 hours of it being available.

After the initial AE/SAE report, the investigator is required to proactively follow each participant at subsequent visits/contacts. All SAEs will be followed until resolution, stabilization, the event is otherwise explained, or the participant is lost to follow-up (as defined in Section 7.3).

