APPENDIX B. CLINICALLY NOTABLE HEMATOLOGIC EVENTS

This appendix provides a list of 3 categories of clinically notable treatment-emergent hematologic events based on customized MQs.

| Adverse Event Category | Preferred Term | Code |
|------------------------|---|----------|
| Anemia | Anaemia macrocytic | 10002064 |
| | Aplasia pure red cell | 10002965 |
| | Aplastic anaemia | 10002967 |
| | Erythroblast count decreased | 10058505 |
| | Erythropenia | 10015287 |
| | Hypoplastic anaemia | 10021074 |
| | Microcytic anaemia | 10027538 |
| | Red blood cell count decreased | 10038153 |
| | Anaemia | 10002034 |
| | Haematocrit decreased | 10018838 |
| | Haemoglobin decreased | 10018884 |
| | Leukoerythroblastic anaemia | 10053199 |
| Neutropenia | Normochromic normocytic anaemia | 10029783 |
| | Agranulocytosis | 10001507 |
| | Band neutrophil count decreased | 10057950 |
| | Febrile neutropenia | 10016288 |
| | Granulocyte count decreased | 10018681 |
| | Granulocytopenia | 10018687 |
| | Neutropenia | 10029354 |
| | Neutropenic infection | 10059482 |
| | Neutropenic sepsis | 10049151 |
| | Neutrophil count decreased | 10029366 |
| Thrombocytopenia | Acquired amegakaryocytic thrombocytopenia | 10076747 |
| | Platelet count decreased | 10035528 |
| | Thrombocytopenia | 10043554 |
| | Plateletcrit decreased | 10064784 |

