APPENDIX F. THROMBOEMBOLIC EVENTS

| Group | Preferred Term | Code | Level | Scope | Category | Weight | Status | Addition Version | Last Modified Version |
|----------|------------------------------------|----------|-------|--------|----------|--------|--------|------------------|-----------------------|
| Arterial | Acute aortic syndrome | 10074337 | PT | Narrow | A | 0 | Active | 17.0 | 17.0 |
| | Acute myocardial infarction | 10000891 | PT | Narrow | A | 0 | Active | 10.0 | 10.0 |
| | Amaurosis | 10001902 | PT | Narrow | A | 0 | Active | 10.0 | 10.0 |
| | Amaurosis fugax | 10001903 | PT | Narrow | A | 0 | Active | 10.0 | 10.0 |
| | Angioplasty | 10002475 | PT | Narrow | A | 0 | Active | 16.0 | 16.0 |
| | Aortic bypass | 10057617 | PT | Narrow | A | 0 | Active | 10.0 | 10.0 |
| | Aortic embolus | 10002897 | PT | Narrow | A | 0 | Active | 10.0 | 10.0 |
| | Aortic surgery | 10061651 | PT | Narrow | A | 0 | Active | 10.0 | 10.0 |
| | Aortic thrombosis | 10002910 | PT | Narrow | A | 0 | Active | 10.0 | 10.0 |
| | Aortogram abnormal | 10057794 | PT | Narrow | A | 0 | Active | 10.0 | 10.0 |
| | Arterectomy | 10071026 | PT | Narrow | A | 0 | Active | 14.0 | 14.0 |
| | Arterectomy with graft replacement | 10003140 | PT | Narrow | A | 0 | Active | 10.0 | 10.0 |
| | Arterial angioplasty | 10081731 | PT | Narrow | A | 0 | Active | 21.1 | 21.1 |
| | Arterial bypass occlusion | 10077766 | PT | Narrow | A | 0 | Active | 19.0 | 19.0 |
| | Arterial bypass operation | 10056418 | PT | Narrow | A | 0 | Active | 10.0 | 10.0 |
| | Arterial bypass thrombosis | 10077765 | PT | Narrow | A | 0 | Active | 19.0 | 19.0 |
| | Arterial graft | 10061655 | PT | Narrow | A | 0 | Active | 10.0 | 10.0 |
| | Arterial occlusive disease | 10062599 | PT | Narrow | A | 0 | Active | 10.0 | 10.0 |
| | Arterial stent insertion | 10061657 | PT | Narrow | A | 0 | Active | 10.0 | 10.0 |
| | Arterial therapeutic procedure | 10052949 | PT | Narrow | A | 0 | Active | 10.0 | 10.0 |
| | Arterial thrombosis | 10003178 | PT | Narrow | A | 0 | Active | 10.0 | 10.0 |
| | Arteriogram abnormal | 10061659 | PT | Narrow | A | 0 | Active | 10.0 | 10.0 |
| | Arteriogram carotid abnormal | 10003195 | PT | Narrow | A | 0 | Active | 10.0 | 10.0 |
| | Arteriotomy | 10078636 | PT | Narrow | A | 0 | Active | 19.1 | 19.1 |
| | Atherectomy | 10063025 | PT | Narrow | A | 0 | Active | 10.0 | 10.0 |
| | Atherosclerotic plaque rupture | 10076604 | PT | Narrow | A | 0 | Active | 18.1 | 18.1 |

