| | Coronary angioplasty | 10050329 | PT | Narrow | A | 0 | Active | 16.0 | 16.0 |
| | Coronary arterial stent insertion | 10052086 | PT | Narrow | A | 0 | Active | 10.0 | 10.0 |
| | Coronary artery bypass | 10011077 | PT | Narrow | A | 0 | Active | 10.0 | 10.0 |
| | Coronary artery embolism | 10011084 | PT | Narrow | A | 0 | Active | 10.0 | 10.0 |
| | Coronary artery occlusion | 10011086 | PT | Narrow | A | 0 | Active | 10.0 | 10.0 |
| | Coronary artery reocclusion | 10053261 | PT | Narrow | A | 0 | Active | 10.0 | 10.0 |
| | Coronary artery surgery | 10011090 | PT | Narrow | A | 0 | Active | 10.0 | 20.1 |
| | Coronary artery thrombosis | 10011091 | PT | Narrow | A | 0 | Active | 16.0 | 16.0 |
| | Coronary endarterectomy | 10011101 | PT | Narrow | A | 0 | Active | 10.0 | 10.0 |
| | Coronary revascularisation | 10049887 | PT | Narrow | A | 0 | Active | 10.0 | 10.0 |
| | Coronary vascular graft occlusion | 10075162 | PT | Narrow | A | 0 | Active | 17.1 | 17.1 |
| | Embolia cutis medicamentosa | 10058729 | PT | Narrow | A | 0 | Active | 10.0 | 10.0 |
| | Embolism arterial | 10014513 | PT | Narrow | A | 0 | Active | 10.0 | 13.1 |
| | Endarterectomy | 10014648 | PT | Narrow | A | 0 | Active | 10.0 | 10.0 |
| | Femoral artery embolism | 10068365 | PT | Narrow | A | 0 | Active | 11.1 | 11.1 |
| | Hepatic artery embolism | 10019635 | PT | Narrow | A | 0 | Active | 10.0 | 10.0 |
| | Hepatic artery occlusion | 10051991 | PT | Narrow | A | 0 | Active | 10.0 | 10.0 |
| | Hepatic artery thrombosis | 10019636 | PT | Narrow | A | 0 | Active | 10.0 | 10.0 |
| | Hypothenar hammer syndrome | 10063518 | PT | Narrow | A | 0 | Active | 10.0 | 10.0 |
| | Iliac artery embolism | 10021338 | PT | Narrow | A | 0 | Active | 10.0 | 10.0 |
| | Iliac artery occlusion | 10064601 | PT | Narrow | A | 0 | Active | 10.0 | 10.0 |
| | Intra-aortic balloon placement | 10052989 | PT | Narrow | A | 0 | Active | 10.0 | 10.0 |
| | Intraoperative cerebral artery occlusion | 10056382 | PT | Narrow | A | 0 | Active | 10.0 | 10.0 |
| | Ischaemic cerebral infarction | 10060840 | PT | Narrow | A | 0 | Active | 10.0 | 10.0 |
| | Ischaemic stroke | 10061256 | PT | Narrow | A | 0 | Active | 10.0 | 10.0 |
| | Lacunar infarction | 10051078 | PT | Narrow | A | 0 | Active | 10.0 | 10.0 |
| | Leriche syndrome | 10024242 | PT | Narrow | A | 0 | Active | 13.1 | 13.1 |
| | Mesenteric arterial occlusion | 10027394 | PT | Narrow | A | 0 | Active | 17.0 | 17.0 |

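### SAP Appendix F omits unqualified stroke and clot terms and Appendix B omits multi-lineage cytopenia terms, so the notable-event tables can under-count participants

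*SAP*

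**What the plan says.** SAP Section 9.2.4 opens with "There are 9 categories of clinically notable TEAEs" and closes its list of them with "thromboembolic events, fungal infections) that, in particular, are of scientific and medical interest specific to itacitinib and the GVHD population". The term lists are in Appendices B to F. For each category the SAP plans the number and percentage of participants with at least one event, and adds: "Summaries of clinically notable AEs based on customized MQs will be provided by category, PT, and the maximum severity". Tables 3.2.23 and 3.2.24 report the hematologic categories, and Tables 3.2.34 and 3.2.35 the thromboembolic category.

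Appendix B introduces itself this way: "This appendix provides a list of 3 categories of clinically notable treatment-emergent hematologic events based on customized MQs". The three are anemia, neutropenia and thrombocytopenia. The list headed "APPENDIX F. THROMBOEMBOLIC EVENTS" has two groups, Arterial and Venous. Its Arterial group includes "Ischaemic stroke". No SAP rule brings an unlisted term into a category.

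Protocol Section 8.3.1 says that adverse events "should be described using a diagnosis whenever possible rather than by individual underlying signs and symptoms".

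**The concern.** A list-based category count is only as complete as its list. If a site reports a stroke without a mechanism, or a clot without the vessel, and it is coded to a general term, Appendix F has no place for it and the participant drops out of the thromboembolic count. If a site follows Protocol Section 8.3.1 and records a fall in several cell lines as one diagnosis, that term may count in none of the three hematologic categories.

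SAP Section 7.2 bases Part 1 expansion dose selection primarily on the incidence and severity of adverse events across cohorts. The general tables do not replace the category count. It is a count of participants with at least one qualifying event, and preferred-term rows cannot be added up to it because one participant can appear in several rows. No other planned table pools the clotting events.

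**Working it through.** This is mainly a check of list content. The plan's own counts come first. Section 9.2.4 states nine categories and names nine: anemia, neutropenia, thrombocytopenia, CMV, EBV, hyperlipidemia, QT prolongation, thromboembolic and fungal. Appendix B states three and has three. Eight of the nine have a list in Appendices B to F. Fungal infections do not and are tied in Appendix A to a MedDRA high-level group term, which is a separate matter.

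**Appendix F.** Both groups run alphabetically to their ends with no sign of redaction, so a missing term can be located by its neighbours:
- Cerebral infarction would fall after Cerebral hypoperfusion, and cerebrovascular accident just before Cerebrovascular insufficiency. These two listed terms are adjacent.
- Stroke would fall between Stress cardiomyopathy and Subclavian artery embolism, which are adjacent.
- Embolism would fall between Embolia cutis medicamentosa and Embolism arterial (Arterial group), or between Deep vein thrombosis postoperative and Embolism venous (Venous group). Both pairs are adjacent. The Venous pair also leaves no room for a device-related thrombosis term, nor does the Arterial pair Coronary vascular graft occlusion and Embolia cutis medicamentosa.
- Thrombosis would fall between Thromboembolectomy and Thrombotic microangiopathy (Arterial), or between Thrombosed varicose vein and Thrombosis corpora cavernosa (Venous). Both pairs are adjacent.

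Some less specific terms are captured. Peripheral embolism, Renal embolism and Splenic embolism (Arterial), and Postoperative thrombosis and Pulmonary thrombosis (Venous), name neither an artery nor a vein. Ischaemic cerebral infarction, Lacunar infarction, Basal ganglia infarction and Transient ischaemic attack are also listed.

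The list is not narrow by design. Its Venous group counts Central venous catheterisation, Compression garment application and Vena cava filter removal. A procedure or garment therefore scores as a thromboembolic event while an unspecified thrombosis does not.

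**Appendix B.** Anemia has 13 terms, Neutropenia 9 and Thrombocytopenia 4. None is pancytopenia, bicytopenia or bone marrow failure. Aplastic anaemia is listed under Anemia only, so it adds nothing to the neutropenia or thrombocytopenia counts.

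**Size.** The documents give no counts for the missing terms, so both rates below are assumptions.
- Group size n = 35 (Protocol Section 10.1.2).
- Assumed thromboembolic incidence p = 5% to 10%.
- Assumed share coded without vessel type u = 10% to 30%.
- Expected participants missed = n × p × u, if each affected participant has one such event.
- Low: 35 × 0.05 × 0.10 = 0.175, about 0.2.
- High: 35 × 0.10 × 0.30 = 1.05, about 1.
- One participant = 1/35 = 2.9 percentage points.

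No comparable range can be built for multi-lineage cytopenias, because the documents give no basis for how often sites would use such a term.

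**The case against.** The strongest reply is that nothing disappears. Every TEAE goes into the SOC and preferred-term tables (Tables 3.2.2 to 3.2.4) and, where it qualifies, into the serious, Grade 3 or higher and fatal tables. An unspecified stroke would be visible there by name. Cytopenias are also captured without any AE coding, through CTCAE-graded hematology shifts (Table 3.3.1.2), and during run-in through DLT rules that use neutrophil and platelet counts directly. No formal test or decision threshold rests on the notable-event tables, and SAP Section 7.2 refers to adverse events overall. All of this stands and limits the point to under-counting within a descriptive category. It does not supply the missing pooled count of participants.

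Three stronger readings are tempting, and the documents do not support them:
- A reader might infer that every clot reported without a vessel type is missed. The captured terms listed above show otherwise.
- A reader might infer from Protocol Section 8.3.1 that a multi-lineage fall would usually be recorded outside all three categories. Protocol Section 9.1, which deals with abnormal laboratory results directly, gives anemia and thrombocytopenia as its example diagnoses, and both are in Appendix B. The Part 1 summary in Protocol Section 2.3.2.1 likewise reports thrombocytopenia and platelet count decrease, both listed. So 'may be missed' is as far as the text goes.
- A reader might infer that the gap hides a dose difference in thrombocytopenia. It was the most common Part 1 TEAE (4 of 11 at 200 mg, 5 of 10 at 300 mg), but SAP Section 1.1 records that the DMC saw no toxicity difference between those doses, and nothing shows that any such event was coded to an unlisted term.

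**Conclusion.** The gap is real and modest. Followed as written, Section 9.2.4 leaves out of the thromboembolic tables any participant whose only event is coded to an unqualified stroke, cerebral infarction, thrombosis, embolism or device-related thrombosis term. It may also leave a multi-lineage cytopenia out of the hematologic tables, with laboratory shifts as partial cover. This assumes that the MedDRA version in use has such terms and that coders use them.

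The thromboembolic range of about 0.2 to 1 participant per group of 35 is illustrative only, because both rates behind it are assumed. A change from 3/35 (8.6%) to 2/35 (5.7%) sits at the top of that range and should not be read as the expected effect. The correction is still worth making: it is cheap, and it makes the table count what its title says.

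**What to change.** 1. In Appendix F, add a third group, 'vessel type unspecified or mixed', holding the unqualified stroke or cerebrovascular accident, cerebral infarction, thrombosis, embolism and device-related thrombosis terms.
2. In Appendix B, add pancytopenia to all three categories. Show terms that do not identify the affected lineage, such as bicytopenia and bone marrow failure, in a separate multi-lineage row. Placing those in every category would assign a lineage, and a maximum grade, that the report does not establish.
3. Re-run both lists against the MedDRA version used at database lock, and state that version. The SAP text gives none, and the newest entries in Appendix F carry version 22.1.

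The cost is two list edits and a query re-run, with no new data. The downside is slightly higher category counts. A footnote should also say that a pancytopenia carries its recorded grade into each of the three categories.

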9.3. Analyses for the Data Monitoring Committee

All safety data will be closely monitored. An external DMC will perform a full review of safety, efficacy, tolerability, and PK data. The primary purpose of the DMC is to provide a recommendation on an appropriate dose of itacitinib for Part 2.

Details of the efficacy evaluation will be included in the internal DMC charter. All safety information, including the AE data from the replaced participants, will be reviewed during this review process.

9.4. Clinical Laboratory Tests

Laboratory values and change from baseline values will be summarized descriptively by visit. Baseline will be determined according to [Section 4.1.3](#). If there are multiple values that meet the criteria for baseline, additional rules may be provided after consultation with the medical monitor to delineate which value will be defined as baseline.

Laboratory data will be classified based on CTCAE grade. The incidence of abnormal laboratory values and shift tables relative to baseline will be tabulated.

9.5. Vital Signs

Descriptive statistics and mean change from baseline will be summarized for vital signs (ie, blood pressure, pulse, respiratory rate, and body temperature) at each assessment time. Vital sign results will be reviewed for abnormalities (see [Table 7](#)), and participants exhibiting vital sign abnormalities will be listed. A value will be considered an "alert" value if it is outside the established range and shows a > 25% change from baseline. The values for participants exhibiting alert vital sign abnormalities will be listed.

Table 7: Criteria for Vital Sign Abnormalities

| Parameter | High Threshold | Low Threshold |
|--------------------------|------------------|-----------------|
| Systolic blood pressure | > 155 mmHg | < 85 mmHg |
| Diastolic blood pressure | > 100 mmHg | < 40 mmHg |
| Pulse | > 100 bpm | < 45 bpm |
| Temperature | > 38°C | < 35.5°C |
| Respiratory rate | > 24 breaths/min | < 8 breaths/min |

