Based on collected data in the GVHD indication, doses of 200 mg and 300 mg QD result in systemic JAK1 inhibition that may have therapeutic benefit and are generally well-tolerated in GVHD patients. Therefore, doses of 200 mg QD and 300 mg QD are being explored in Part 1 of this study.

2.3.2.1. Preliminary Results From Part 1

Preliminary data from Part 1 was reviewed by an independent DMC. At the data cutoff date for the DMC review (20 SEP 2019), 21 participants had been enrolled in the study in the 200 mg QD dose cohort (n = 11) or 300 mg QD dose cohort (n = 10); of them, 20 participants (10 in each dose cohort) had completed 28 days on study at that timepoint. The median duration of exposure was 50 days (range: 5-246 days) in the 200 mg dose cohort and 70 days (range: 29-200 days) in the 300 mg dose cohort.

The most common TEAEs were thrombocytopenia/platelet count decrease reported in 9 of 21 participants (43%), including 4 of 11 participants (36%) in the 200 mg dose cohort and 5 of 10 participants (50%) in the 300 mg dose cohort. The most commonly reported nonhematologic TEAEs were muscular weakness (24%), CMV infection, diarrhea, fatigue, headache, pyrexia, and blood creatinine increased (19% each). The frequency of these events were generally consistent across dose cohorts. A total of 5 participants (3 in the 200 mg dose cohort and 2 in the 300 mg dose cohort) experienced an AE that led to itacitinib interruption, specifically, platelet count decrease (2 participants) and febrile neutropenia, pneumonia, sinusitis, and hyperkalemia (1 participant each). TEAEs that required itacitinib dose reduction were reported in 4 participants (2 participants in each dose cohort) and was thrombocytopenia/platelet count decrease in all cases, associated with microangiopathy in 1 participant. One participant in the 200 mg dose cohort discontinued itacitinib due to Grade 3 thrombocytopenia.

Dose-limiting toxicities as assessed by investigator were Grade 3 hyperkalemia in 1 participant with pre-existing hyperkalemia at baseline enrolled in the 200 mg dose cohort and Grade 4 thrombocytopenia in 1 participant enrolled in the 300 mg dose cohort.

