8.3.3. Vital Signs

Vital sign measurements include blood pressure, pulse, respiratory rate, body temperature, and weight. Height will also be measured at screening. Blood pressure and pulse will be taken with the participant in the recumbent, semirecumbent, or sitting position after 5 minutes of rest. Abnormal vital sign results identified after the first dose of study treatment constitute an AE if they are considered clinically meaningful, induce clinical signs or symptoms, require concomitant therapy, or require changes in study treatment.

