4.1.3. Baseline Value

Baseline is the last nonmissing measurement obtained before the first administration of study treatment (eg, itacitinib with corticosteroids or corticosteroids only). When itacitinib and corticosteroids are started on different days, then the rules mentioned in Section 4.1.1 will be followed.

When scheduled assessments and unscheduled assessments occur on the same day, and time of the assessment or time of first dose is not available, use the following convention to determine baseline:

- If both a scheduled and an unscheduled visit are available on the day of the first dose and the time is missing, use the scheduled assessment as baseline.
- If all scheduled assessments are missing on the day of the first dose and an unscheduled assessment is available, use the unscheduled assessment as baseline.

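### The SAP's vital-sign alert rule asks for a change of more than 25% from baseline, which no fever in °C can reach, so the temperature alert tier will contain no fevers by construction.

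*SAP*

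**What the plan says.** SAP 9.5 sets up two tiers.

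- Abnormality tier: "Vital sign results will be reviewed for abnormalities (see [Table 7](#)), and participants exhibiting vital sign abnormalities will be listed". Table 7 gives the limits, which for temperature are above 38°C and below 35.5°C. This tier has no percent-change condition.
- Alert tier: a value must be "outside the established range and shows a > 25% change from baseline". Both conditions are required, and the sentence applies to every Table 7 parameter: systolic and diastolic pressure, pulse, temperature and respiratory rate. For this tier the output is described differently: "The values for participants exhibiting alert vital sign abnormalities will be listed".

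The reference value comes from SAP 4.1.3: "Baseline is the last nonmissing measurement obtained before the first administration of study treatment".

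Abnormal vital signs also have a separate route into the safety data. Protocol 8.3.3 states: "Abnormal vital sign results identified after the first dose of study treatment constitute an AE if they are considered clinically meaningful". It goes on to name other grounds, such as the need for concomitant therapy. None of them is a percent change.

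**The concern.** An alert tier is meant to pick out the more marked abnormalities. Asking for a large relative change as well as an out-of-range value can do that for a quantity with a true zero, such as pulse or blood pressure. Celsius has an arbitrary zero and body temperature varies over a narrow band, so a 25% change corresponds to roughly 9°C. The condition cannot separate a marked fever from a slight one. It removes both.

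Fever is of interest in this trial. Participants receive a JAK inhibitor with corticosteroids after transplantation. Protocol 2.4 names infection as a risk to be managed, and Protocol 2.3.2.1 reports pyrexia in 19% of Part 1 participants. An alert listing that shows blood pressure and pulse but no temperatures could be taken as a finding about fever, when it is a consequence of the definition.

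**Working it through.** The plan states no derived figure to reproduce. The check is direct arithmetic on the rule.

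**Inputs.** From SAP 9.5: the 25% condition and the Table 7 limits. From SAP 4.1.3: the definition of baseline. Assumption: baseline temperature lies within the Table 7 range, 35.5 to 38.0°C, since the documents give no baseline temperatures. The SAP gives no direction for the change, so both directions are checked.

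**Formula.** Percent change = 100 × (value − baseline) / baseline. The 25% condition therefore requires value > 1.25 × baseline or value < 0.75 × baseline.

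**Step 1. Reading needed for a temperature alert.**

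| Baseline (°C) | High alert needs above | Low alert needs below |
|---|---|---|
| 35.5 | 1.25 × 35.5 = 44.375 | 0.75 × 35.5 = 26.625 |
| 36.5 | 1.25 × 36.5 = 45.625 | 0.75 × 36.5 = 27.375 |
| 37.0 | 1.25 × 37.0 = 46.25 | 0.75 × 37.0 = 27.75 |
| 38.0 | 1.25 × 38.0 = 47.5 | 0.75 × 38.0 = 28.5 |

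All of these lie well outside the Table 7 limits, so the 25% condition alone decides the outcome and the limits of 38°C and 35.5°C play no part.

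**Step 2. How far clinical readings fall short.** From 37.0°C:

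- 38°C is +2.7%
- 40°C is 100 × 3 / 37 = +8.1%
- 42°C is 100 × 5 / 37 = +13.5%
- 35.5°C is −4.1%
- 32°C is −13.5%

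The in-range baseline most favourable to a high alert is 35.5°C. Even from there, 42°C is only 100 × 6.5 / 35.5 = +18.3%.

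**Step 3. Baseline needed for a fever to qualify.** A reading just above 38°C needs a baseline below 38 / 1.25 = 30.4°C. A reading of 40°C needs one below 40 / 1.25 = 32.0°C. A reading just below 35.5°C needs a baseline above 35.5 / 0.75 = 47.3°C.

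**Step 4. The same rule for the other parameters.** A reading just beyond the Table 7 limit is an alert when baseline is:

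| Parameter | High limit | Baseline below about | Low limit | Baseline above about |
|---|---|---|---|---|
| Systolic pressure (mmHg) | 155 | 155 / 1.25 = 124 | 85 | 85 / 0.75 = 113.3 |
| Diastolic pressure (mmHg) | 100 | 100 / 1.25 = 80 | 40 | 40 / 0.75 = 53.3 |
| Pulse (bpm) | 100 | 100 / 1.25 = 80 | 45 | 45 / 0.75 = 60 |
| Respiratory rate (breaths/min) | 24 | 24 / 1.25 = 19.2 | 8 | 8 / 0.75 = 10.7 |

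These are ordinary baselines. The rule works for four parameters and fails for the fifth.

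**Step 5. Dependence on the unit.** A rise from 37 to 40°C is +8.1% in Celsius. The same rise in Fahrenheit is 98.6 to 104.0, or 100 × 5.4 / 98.6 = +5.5%. A criterion whose result changes with the unit is not measuring the size of the change.

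**The case against.** The strongest reply is that little is lost. The sentence before the alert rule lists participants with any Table 7 abnormality, without a percent-change condition, so everyone with a temperature above 38°C or below 35.5°C is identified. Clinically meaningful fever is an adverse event under Protocol 8.3.3, and Part 1 shows that the route works, since pyrexia was reported. Adverse event incidence and severity is the primary endpoint of the Part 1 expansion. Infections have their own outputs in SAP 9.2.4 and Appendix A, including a table of Grade 3 or higher infections. Temperature is summarized at each assessment (Table 3.4.5). No dose-limiting toxicity definition, stopping boundary, dose modification or DMC trigger refers to the alert tier. All of this stands, and it is why the point is minor.

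A reader might infer that no fever or hypothermia can be flagged anywhere in this trial. The documents do not support that: the abnormality tier and adverse event reporting both capture such readings. A reader might also infer that a temperature alert is strictly impossible. That is also too strong, because a reading below about 27 to 28°C from a normal baseline would satisfy the rule as written.

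Two limits on the reply remain. First, SAP 9.5 promises a listing of participants for abnormalities but of values only for alerts, so on a literal reading it assigns fever values to neither listing. Second, Appendix A names no vital-sign listing of either kind. That does not show that none will be produced, but it leaves the fallback unspecified.

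**Conclusion.** The alert rule is wrong as written for temperature. With a baseline of 35.5 to 38.0°C, an alert needs a reading above 44.4 to 47.5°C or below 26.6 to 28.5°C, so the alert tier will contain no fevers whatever the data show. The result rests on the assumed baseline range and on the ordinary understanding that fever does not reach 44°C. It is not sensitive to the first assumption, since a 40°C reading would qualify only from a baseline below 32.0°C.

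The consequence is confined to one descriptive safety output. Participants with out-of-range temperatures remain identifiable, and no estimate, test, sample size or decision rule changes. Severity is minor.

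**What to change.** Amend the alert sentence in SAP 9.5 so that the 25% criterion applies to blood pressure, pulse and respiratory rate only. Define a temperature alert as a value outside the Table 7 range that also differs from baseline by a prespecified absolute amount in °C, with the amount set by the sponsor before the listing is produced. Using the Table 7 range alone would also remove the fault, but it would select the same participants as the abnormality listing and add only their values.

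In the same edit, name the abnormality and alert listings in Appendix A and say whether the abnormality listing shows values.

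The cost is one sentence in the SAP, two entries in Appendix A and a small programming change. No new data are needed. If the listing has already been produced, a footnote saying that the 25% condition excludes fever by definition would prevent a misreading.
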